2 STUDY OBJECTIVES AND ENDPOINTS

2.1 Study Objectives and Endpoints

Primary Objective	Primary Endpoint
• To evaluate the PK of oral (po) only omadacycline in adults with CABP.	The following plasma PK parameters will be determined:
	 Area under the plasma concentration time curve (AUC) from time 0 to 48 hours after dosing (AUC₀₋₄₈)
	• Area under the plasma concentration time curve (AUC) from time 0 to 24 hours after dosing (AUC ₀₋₂₄)
	• AUC from time 0 to the last quantifiable concentration (AUC _{last})
	• Maximum observed plasma concentration (C _{max})
	• Time to reach maximum observed plasma concentration (T _{max})
	• Elimination half-life associated with the terminal slope of the semilogarithmic concentration-time curve $(T_{1/2})$
Secondary Objective	Secondary Endpoint
• To evaluate the safety of omadacycline in the treatment of adults with CABP.	The following variables will be analyzed descriptively in the Safety population:
	• Adverse Events (AEs), and Serious Adverse Events (SAEs)
	• Vital signs (systolic and diastolic BP, pulse/heart rate, body temperature, pulse oximetry, RR), including change from Baseline by time point measured
	• Clinically notable vital signs (meeting predefined criteria as specified in the SAP) by time point measured
	• Laboratory parameters (Hematology and Serum Chemistry), including change

	 from Baseline by visit and overall worst post-baseline Clinically notable laboratory parameters (meeting predefined criteria as specified in the SAP) by visit and overall worst post-baseline Concomitant Medications Urinalysis and Pregnancy assessments (Screening only)
Exploratory Objectives	
Exploratory Objectives	Exploratory Endpoint

3 STUDY DESIGN

This is an open-label Phase 1b study evaluating oral omadacycline in the treatment of adults with CABP.

This study is intended to evaluate the PK of an oral dosing regimen in adults with CABP. Subjects will initiate treatment with an oral loading dose of 300 mg BID on Day 1 followed by 300 mg on subsequent days.

Following a screening period of up to 24 hours, eligible subjects will be assigned to receive 7 to 10 days of po treatment. Subjects with baseline bacteremia (i.e., confirmed from local blood culture drawn at screening) can receive up to 14 days of treatment after consultation with the medical monitor.

Subjects may receive oral treatment in either inpatient or outpatient settings, provided that all assessments can be completed at the timepoints required by protocol.

Test Article	Study Day	Study Day	Study Days
	1	2	3-10
Omadacycline	300 mg po BID	300 mg po QC	300 mg po QC

Eligible subjects will be assigned to the following treatment groups.

po = per oral, a dosing day is a 24-hour day not a calendar day

a The total duration of treatment is 7 to 10 days. Treatment duration can be extended to up to 14 days for subjects with bacteremia that, in the opinion of the investigator, requires more than 10 days of treatment.

Refer to the Schedule of Events (Appendix 1) for the summary of subject visits and assessments through end of treatment (EOT).

Subjects will return to the study site for a Post Therapy Evaluation (PTE) 5 to 10 days after the last dose of test article. A Final Follow-up visit (FFU) will be conducted within 30 to 37 days following the first dose of test article. The FFU assessment may be conducted via telephone contact or by another interactive technology for subjects who had an outcome of Clinical Success in the opinion of the investigator at EOT and PTE and had no AEs or clinically significant laboratory or electrocardiogram (ECG) abnormalities noted at or after the PTE visit. Otherwise, this assessment is to be performed with an in-person study visit.

Subjects will participate in the study for up to 37 days. Following a screening period of up to 24 hours, eligible subjects will be assigned to receive treatment. Eligible subjects will be assigned to receive 7 to 10 days of po treatment. Subjects with baseline bacteremia (i.e., confirmed from local blood culture drawn at screening) can receive up to 14 days of treatment after consultation with the medical monitor.

The study is expected to be complete in approximately 6 months.

4 ASSESSMENT OF CABP SYMPTOM SEVERITY FOR EFFICACY

The investigator will specifically assess the presence and severity level of the subject's symptoms of cough, sputum production, pleuritic chest pain, and dyspnea on a 4-point scale (absent, mild, moderate, or severe) based upon the Community Acquired Bacterial Pneumonia Subject Symptom Severity Guidance Framework for Investigator Assessment (see Protocol Appendix 2) and enter the symptom severity level into the eCRF. Subjects must have at least 3 of these 4 symptoms of CABP to be eligible for the study.

5 GENERAL STATISTICAL CONSIDERATIONS

All data collected will be presented in data listings. Data from subjects excluded from an analysis population will be presented in the data listings, but not included in the calculation of summary statistics.

For categorical variables, frequencies and percentages will be presented. Continuous variables will be summarized using descriptive statistics (number of subjects, mean, median, standard deviation [SD], minimum, and maximum).

During the analysis and reporting process, any deviations from the statistical analysis plan designed for this protocol will be described and justified in the final clinical study report (CSR).

Unless specified otherwise, baseline will be defined as the last non-missing assessment prior to the study drug administration for each treatment period. Unscheduled visits will be used in determining baseline.

Missing values will not be imputed for safety endpoints. The handling rule for missing PK concentration will be described in Section 6.2.

5.1 Sample Size Determination

This study is designed to evaluate the PK profile of an oral dosing regimen, 300mg BID on Day 1 and QD on Day 2, in adults with CABP. The sample size determination is based on consideration of the precision of the estimate, GMR of AUC (0-48) for 300mg po to 100mg IV, derived from model-based simulations of omadacycline concentration data (Phase I studies).

With 20 subjects evaluable for PK population, there will be 90% probability that the 90% CIs of the GMR for AUC $_{(0-48)}$ will be within 80% and 125%. Up to 30 subjects will be enrolled so that at least 20 subjects are evaluable for bioavailability estimation.

The total number of subjects may be adjusted to ensure that there are 20 subjects evaluable for PK population.

5.2 Study Analysis Populations

5.2.1 Intent-to-Treat (ITT) Population

The ITT population will consist of all enrolled subjects regardless of whether the subject received test article.

5.2.2 Safety (SAF) Population

The Safety population will consist of all enrolled subjects who receive test article. All safety analyses will be conducted in this population.

5.2.3 Pharmacokinetic (PK) Population

The pharmacokinetic population is defined as subjects who receive test article and have at least 1 evaluable PK parameter. If any subject has an emesis within 4 hours after dosing, the subject will be excluded from PK Analysis. If any subject discontinues dosing before 48 hours with incomplete PK profile for 0-24 or 0-48 hours, the subject will be excluded from the PK analysis for AUC_{0-24} and AUC_{0-48} , respectively.

This population will be used for listings, summary tables, and plotting of individual and mean/median concentration-time profiles.

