4 STUDY OBJECTIVES

4.1 **Primary Objective**

The primary objective of this study is:

• To evaluate the PK of oral (po) only omadacycline in adults with CABP.

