12.3 Analysis Populations

The following subject analysis populations have been defined for the various analyses of PK, safety and efficacy:

- The PK population will consist of all assigned subjects who receive test article and have PK samples collected.
- The Safety population will consist of all assigned subjects who receive at least one dose of test article.
- The intent-to-treat (ITT) population will consist of all assigned subjects.

Additional populations may be defined in the SAP as appropriate.

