7.3 Treatment Comparison

The comparison of interest is the comparative bioavailability assessment between the test, 300mg po in CABP patients, and the reference, 100mg IV in healthy subjects. The comparison will be based on 90% confidence intervals (CIs) for the geometric mean ratios (GMR) of AUC (0-48) for the two dosing regimens being within 80% and 125%.

The PK parameter data for 100mg IV in healthy subjects comes from PTK 0796-SDES-0501(n=5), PTK 0796-BEQU-0801(n=11), PTK 0796 WOIV-0703(n=12), CPTK796A2104(n=21), CPTK796A2201(n=6), PTK 0796-RENL-15102(n=8). Using the

day 1 plasma concentration profile of the 100mg IV QD dosing from these studies, a BID dosing on day 1 and a QD dosing on day 2 was simulated using the superposition principle. The simulation model-based AUC $_{(0-48)}$ characteristics for each study are shown in the table below:

Study	n	Mean ln (AUC (0-48))	SD ln (AUC (0-48))
SDES-0501	5	9.5968	0.1896
BEQU-0801	11	9.8702	0.1467
WOIV-0703	12	10.017	0.1630
A2104	21	10.043	0.1649
A2201	6	10.129	0.1752
RENL-15102	8	10.039	0.1838
Total	63	9.9800	0.2091

The 90% CI of the GMR will be formed as follows: let \bar{y} , *s*, and *n* represent the average, standard deviation, and sample of the log (AUC (0-48)) data observed in the current study. The

pooled standard deviation is $s_p = \sqrt{\frac{(63-1)0.2091117^2 + (n-1)s^2}{63+n-2}}$; the number of degrees of freedom is df = 63 + n - 2; and critical value for the CI is 95th percentile of a t-distribution, $t_{df.0.95}$. The 90% confidence interval on the log scale is

$$\bar{y} - 9.980044 \pm t_{df,0.95} s_p \sqrt{\frac{1}{63} + \frac{1}{n}} = (Lower, Upper)$$

and the CI for the GMR is $(e^{Lower}, e^{Upper}) \times 100\%$.

The following SAS code will be used:

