12 CHANGES FROM THE PROTOCOL

In the protocol, the PK Analysis Set was defined to include subjects who receive omadacycline and have PK samples collected. If any subject has an emesis within 2.5 x median T_{max} after dosing, the subject may be excluded from PK Analysis Set. In the SAP, the PK Analysis Set has been defined to include subjects who receive study drug and have at least 1 evaluable PK parameter. If any subject has an emesis within 4 hours after dosing, the subject will be excluded from PK Analysis Set.

Any changes from this statistical analysis plan will be documented in the CSR for this study.

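### The only planned AUC(0-48) ratio against IV leaves out subjects with early emesis, so it may overstate exposure in patients who start the oral-only regimen

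*SAP*

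**What the plan says.** The primary objective is "To evaluate the PK of oral (po) only omadacycline in adults with CABP" (Protocol 4.1). SAP 7.3 compares the oral regimen in patients with "the reference, 100mg IV in healthy subjects" and judges it on "90% confidence intervals (CIs) for the geometric mean ratios (GMR) of AUC (0-48) for the two dosing regimens being within 80% and 125"%.

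On who enters that comparison:

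- Protocol 12.3: "The PK population will consist of all assigned subjects who receive test article and have PK samples collected". This definition contains no emesis rule.
- SAP 5.2.3: "If any subject has an emesis within 4 hours after dosing, the subject will be excluded from PK Analysis". The rule names no dose and no study day.
- SAP 12 declares the rule as a change. It describes the protocol's rule as discretionary ("the subject may be excluded from PK Analysis Set") and the SAP's as mandatory.
- SAP 7.2 lists and summarises AUC and Cmax for the PK set only. SAP 7.3 defines a single GMR interval.

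Subjects with early emesis do appear elsewhere. SAP 7.1 lists individual concentrations and plots individual profiles for the Safety set, and SAP 6.1 tabulates and lists reasons for exclusion from each population. SAP 5.2.3, however, assigns listings and individual plots to the PK population, so the two sections do not agree on this.

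On numbers, SAP 5.1 says: "Up to 30 subjects will be enrolled so that at least 20 subjects are evaluable for bioavailability estimation". The total may be adjusted to reach 20.

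**The concern.** When two oral products are compared, dropping subjects who vomit is routine, because emesis disturbs both arms and says little about the formulations. Here the reference exposure comes from IV infusion, which vomiting cannot reduce. Any loss falls on the oral side alone, and it is part of what an oral-only regimen delivers to sick patients.

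The exclusion also follows an event that can lower the measured outcome. Since enrolment may be adjusted until 20 are evaluable, excluded subjects can be made up by subjects who did not vomit. The 90% interval could then sit inside 80-125% for patients who kept the drug down, and no planned interval would show whether the same is true of those who started the regimen.

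The open wording of the rule has a second effect. Read literally, emesis after a dose given later than 48 h removes a subject whose AUC(0-48) was untouched.

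**Working it through.** **Inputs from the documents.** Reference n = 63, mean ln AUC(0-48) 9.980044, SD 0.2091117; interval with pooled SD, 63 + n − 2 degrees of freedom and the 95th percentile of t (all SAP 7.3). Target 20 evaluable, up to 30 enrolled (SAP 5.1). Oral bioavailability 34% (Protocol 12.5.1), so the expected GMR is 0.34 × 300/100 = 1.02.

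**Assumptions, not in the documents.** Half-life 12-24 h with first-order loss; number vomiting k of N; each vomiting subject loses one full dose or half a dose; between-subject SD in patients equal to 0.2091.

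**1. The plan's own figures.** The six study rows in SAP 7.3 combine to mean 9.9801 and SD 0.2092, which agrees with the stated total apart from rounding. SAP 5.1 says "there will be 90% probability that the 90% CIs of the GMR for AUC" over 0-48 h will lie within the limits with 20 evaluable subjects. That figure cannot be reproduced, because neither the assumed true GMR nor the patient SD is given. With SD 0.2091 and GMR 1.00 the SAP 7.3 interval gives 98.7% (reference treated as random) to 99.6% (reference fixed). About 90% appears with a patient SD of about 0.30-0.33 at GMR 1.00-1.02.

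**2. Room below 1.** For n = 20 and pooled SD 0.2091, the half-width on the log scale is 1.664 × 0.2091 × √(1/63 + 1/20) = 0.0893. The smallest observed GMR that passes is 0.80 × e^0.0893 = 0.875.

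**3. Share of AUC(0-48) from each dose.** Doses at 0, 12 and 24 h contribute in proportion to 1 − 2^(−48/t), 1 − 2^(−36/t) and 1 − 2^(−24/t) for half-life t.

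- t = 12 h: 0.9375, 0.875, 0.75; shares 37%, 34%, 29%.
- t = 24 h: 0.75, 0.646, 0.5; shares 40%, 34%, 26%.

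One dose is therefore worth 26-40% of AUC(0-48).

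**4. Shift in the GMR.** If r is a vomiting subject's AUC(0-48) relative to the others, then GMR(all) / GMR(no emesis) = r^(k/N), with r = 1 − 0.264 to 1 − 0.396 for a full dose.

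| Vomiting | Full dose lost | Half a dose lost |
|---|---|---|
| 2 of 22 | 3-4% lower | 1-2% lower |
| 5 of 25 | 6-10% lower | 3-4% lower |
| 10 of 30 | 10-15% lower | 5-7% lower |

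**5. Does the verdict change?** Keeping these subjects also widens the interval. With f = k/N, the patient variance becomes 0.2091² + N f(1 − f)(ln r)²/(N − 1). For 5 of 25 with r = 0.6045 this is 0.0437 + 0.0422 = 0.0860. The pooled SD is √[(62 × 0.0437 + 24 × 0.0860)/86] = 0.236, the half-width 1.663 × 0.236 × 0.2364 = 0.093, and the expected lower limit at a no-emesis GMR of 1.00 is 0.904 × e^(−0.093) = 0.82.

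Expected lower limits computed in the same way, for a no-emesis GMR of 1.00-1.02:

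- 2 of 22, full dose: 0.87-0.91.
- 5 of 25, full dose: 0.82-0.88.
- 10 of 30, full dose: 0.83-0.85 at 26% loss, 0.77-0.79 at 40% loss.
- All half-dose cases: at least 0.86.

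Only 10 of 30 at the largest loss falls below 0.80.

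Simulating the SAP 7.3 interval with the reference fixed and each vomiting subject losing 36% gives these probabilities of meeting 80-125%:

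| GMR without emesis | Excluded (n = 20) | Kept, 2 of 22 | Kept, 5 of 25 |
|---|---|---|---|
| 1.00 | 99.6% | 98% | 85% |
| 0.95 | 96% | 82% | 43% |

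**The case against.** The main analysis is defensible. SAP 7.3 calls this a comparative bioavailability assessment, and its reference is itself idealised: IV Day 1 profiles superposed, with every dose fully delivered. An oral estimate from doses that were retained is a coherent counterpart. The rule is prespecified, and SAP 12 discloses it, as Protocol 12.1 allows. All of this stands, and it is why the exclusion can stay in the main analysis.

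Four stronger readings are tempting, and the documents do not support them.

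- **That the GMR does overstate exposure.** Upward is the expected direction, not an established fact. It needs at least one exclusion for emesis that lowered AUC(0-48), and emesis late in a 4-hour window may cost little. No rate or loss is given.
- **That these subjects vanish from the report.** Raw concentrations and exclusion reasons are planned outputs. What is missing is their derived AUC and any GMR that includes them.
- **That the 80-125% verdict would flip.** With a no-emesis GMR of 1.00-1.02 the expected lower limit fails only when all 10 places between 30 enrolled and 20 evaluable are lost to emesis at the largest loss. That allowance must also cover incomplete sampling and withdrawals.
- **That the SAP departed from the protocol silently.** It did not. The remaining loose end is that SAP 12 credits the protocol with a rule based on median Tmax that Protocol 12.3, as supplied, does not contain; the two should be reconciled.

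**Conclusion.** The concern holds in a limited form. The only planned GMR estimates AUC(0-48) given no emesis within 4 hours of a dose, and because the comparator is IV it may overstate exposure in patients who start the oral-only regimen. No planned AUC or GMR output would show by how much.

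Under the stated assumptions the gap is about 1-4% with 2 of 22 vomiting and 3-10% with 5 of 25, across half and full dose loss, and nil if nobody vomits. A change in the 80-125% conclusion is likely only if vomiting is frequent or the GMR without emesis is already below 1. The half-life, the emesis counts, the loss per event and the patient SD are all assumed. This is a worthwhile, inexpensive improvement and not a flaw that invalidates the main analysis.

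**What to change.** - **SAP 5.2.3:** keep the emesis exclusion for the main analysis, but state that for AUC(0-48) it applies only to emesis after the doses given within 0-48 h.
- **SAP 7.3:** add one prespecified sensitivity analysis, the same 90% interval for AUC(0-48) in all dosed subjects with an evaluable 0-48 h AUC, regardless of emesis. Say how this set relates to the withdrawal rule in SAP 10.1.
- **SAP 7.2:** list the AUC(0-48) of each subject excluded for emesis.
- **Those who vomited and then stopped before 48 h:** describe them separately. They have no complete 0-48 h profile, so the sensitivity interval will not include them.

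The cost is one table row and one listing. No new data are needed: the samples are already scheduled, and SAP 8.1 already uses adverse event start times. The downside is an interval that may be lower and wider than the main one. The text should be settled before database freeze, so that the choice is not made after the data are seen.

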6 STUDY POPULATION SUMMARIES

6.1 **Disposition**

The number of subjects included in each of the analysis populations (i.e., ITT, Safety, and PK) will be summarized. A table will summarize the reasons for exclusion from each population and a listing will be provided that indicates each subject's inclusion in/exclusion from the populations and the reason for exclusion from each of the populations.

A listing will be provided of enrolled subjects who did not meet all inclusion/exclusion criteria, and which criteria were not met. The number and percentage of subjects completing the study (defined as receiving at least 1 dose of test article and returning for all the EOT, PTE, and Follow-up Visits), not completing the study, missing each of the EOT and PTE Visits, and prematurely discontinuing from test article will be presented for the ITT population. Reasons for premature discontinuation of test article, not completing the study, and for missing each of the visits, as recorded on the eCRF will be summarized (number and percentage) for the ITT populations. A listing of all subjects who prematurely discontinued from test article or not completing the study will be presented, and the primary reason for discontinuation of test article or not completing the study, as well as the visit(s) missed and the reason for missing the visit(s), will be provided.

6.2 Demographics and Baseline Characteristics

Except where indicated, demographic data and baseline characteristics will be presented for the ITT population. A table will present the subject demographics (e.g., gender, age, ethnicity, and race) and baseline characteristics (height, weight, BMI, and creatinine clearance categorized before the start of test article as:

- severe renal impairment [< 30 mL/min],
- moderate renal impairment [30-50 mL/min],
- mild renal impairment [> 50-80 mL/min], and
- normal renal function [> 80 mL/min]).

Age will be calculated from the date of birth to the informed consent date. Age will be summarized as a continuous variable and in the categories, 18-45, >45-65, and >65 years.

Creatinine clearance will be calculated from the local laboratory data since these data were used for determination of the inclusion and exclusion criteria and will be determined from the Cockcroft-Gault equation.

A table will provide the frequency counts and percentages for subjects who received prior antibiotics, and PORT Risk Class (from the eCRF) for the ITT population. PORT score will also be summarized as a continuous variable.

Baseline assessments of clinical symptoms, clinical signs, abnormal vital signs, and abnormal laboratory signs of CABP will be presented for the ITT, and PK populations.

The number and percentage of subjects with each of the CABP symptoms (cough, pleuritic chest pain, dyspnea, and phlegm/sputum production) by severity (absent, mild, moderate, severe) will be presented. The number and percentage of subjects with the presence by severity (i.e., absent, mild, moderate, severe) of the following clinical signs will be provided: rales, rhonchi, dullness on percussion, bronchial breath sounds, wheezing, decreased breath sounds, and egophony. The number and percentage of subjects with fever (defined as body temperature > 38°C [100.4°F] oral or rectal), hypothermia (defined as body temperature < 36°C [95.5°F] oral or rectal), hypotension with systolic blood pressure < 90 mmHg, heart rate > 90 bpm, respiratory rate > 20 breaths/min, hypoxemia (defined as PaO₂ < 60 mmHg by arterial blood gas or oxygen saturation < 90% by pulse oximetry), elevated total WBC count (> 12,000 cells/mm³), leucopenia (WBC < 4,000 cells/mm³), elevated immature neutrophils (> 15% band forms regardless of total peripheral WBC count) and any of elevated total WBC count, leucopenia or elevated immature neutrophils will be summarized.

Risk factors for CABP will be presented for the ITT population. Risk factors include smoking (current, past, and descriptive statistics of the number of years since quitting for those subjects who were previous smokers), receipt of pneumococcal vaccine, prior lung infection, whether the subject had mild to moderate COPD, symptomatic asthma with wheezing, and chronic cough with or without sputum production.

Readings of baseline chest radiographs, including the type of assessment (CXR or CT scan), presence of pleural effusion, whether the pleural effusion is unilateral or bilateral, whether the pulmonary infiltrate was uni- or multi-lobar and the location of the pulmonary infiltrate (combining left upper lobe and lingula) will be summarized for all subjects in the ITT population.

A listing will be provided that includes all baseline microbiology isolates.

